6.4.8 Day 180 (±7 Days)

The following procedures will be performed at Day 180:

- Determine NIHSS score:
 - Note: NIHSS assessments are preferred to be completed in a face-to-face setting. If conducted remotely, telemedicine is acceptable, and telephone is not acceptable. NIHSS assessments for post-Baseline visits must be completed by staff who are certified in NIHSS administration. Effort should be made to have the same assessor complete all post-Baseline visit assessments for an individual subject when possible. The possibility of a remote visit and the procedures to be conducted need to be discussed with the Sponsor in advance;
- Determine mRS score;
 - Note: mRS assessments are strongly preferred to be completed in a face-to-face setting. If face-to-face assessment is not possible, assessments may be conducted remotely by telemedicine. Only as a last resort in extraordinary circumstances, if telemedicine is not possible, telephone assessment is permitted. Effort should be made to have the same assessor complete all post-Baseline visit assessments for an individual subject when possible. When evaluating subjects to determine the mRS score, the raters of the score must not make any attempt to exclude or correct for disability that the rater attributes to causes other than stroke. The score should be recorded without regard to the cause of the disabilities that impact the score or the time point at which the disabilities occurred. The possibility of a remote visit and the procedures to be conducted need to be discussed with the Sponsor in advance;
- Determine Barthel Index score;
 - Note: Barthel Index assessments are strongly preferred to be completed in a face-to-face setting. If face-to-face assessment is not possible, assessments may be conducted remotely by telemedicine. Only as a last resort in extraordinary circumstances, if telemedicine is not

possible, telephone assessment is permitted. Effort should be made to have the same assessor complete all post-Baseline visit assessments for an individual subject when possible. The possibility of a remote visit and the procedures to be conducted need to be discussed with the Sponsor in advance;

- Record the date the subject was admitted to and/or discharged from the ICU, the hospital, and to a non-hospital residential care facility following the initial stroke;
- Inquire about rehabilitation activities (e.g., inpatient physical therapy, outpatient physical therapy, etc.); and
- Assess adverse events.

6.5 Day 365 (±7 Days)/Early Termination Visit and Withdrawal Procedures

The end of treatment for subjects completing the study is Day 365. For subjects who are withdrawn from the study prior to completion, all Day 365 procedures will be performed at the ET Visit.

Note: The post-infusion visits may be conducted remotely if the subject is unable to attend the site visit. It is preferable to perform a remote visit rather than have the subject miss the visit; the possibility of a remote visit and the procedures to be conducted need to be discussed with the Sponsor in advance.

The procedures to be conducted at Day 365/ET include the following:

- Perform a physical examination;
- Obtain vital signs;
- Perform pulse oximetry;
- Determine NIHSS score;
 - Note: NIHSS assessments are preferred to be completed in a face-to-face setting. If conducted remotely, telemedicine is acceptable, and telephone is not acceptable. NIHSS assessments for post-Baseline visits must be completed by staff who are certified in NIHSS administration. Effort should be made to have the same assessor complete all post-Baseline visit assessments for an individual subject when possible. The possibility of a remote visit and the procedures to be conducted need to be discussed with the Sponsor in advance;

• Determine mRS score:

Note: mRS assessments are strongly preferred to be completed in a face-to-face setting. If face-to-face assessment is not possible, assessments may be conducted remotely by telemedicine. Only as a last resort in extraordinary circumstances, if telemedicine is not possible, telephone assessment is permitted. Effort should be made to have the same assessor complete all post-Baseline visit assessments for an individual subject when possible. When evaluating subjects to determine the mRS score, the raters of the score must not make any attempt to exclude or correct for disability that the rater attributes to causes other than stroke. The score should be recorded without regard to the cause of the disabilities that impact the score or the time point at which the disabilities occurred. The possibility of a remote visit and the procedures to be conducted need to be discussed with the Sponsor in advance;

- Determine Barthel Index score;
 - Note: Barthel Index assessments are strongly preferred to be completed in a face-to-face setting. If face-to-face assessment is not possible, assessments may be conducted remotely by telemedicine. Only as a last resort in extraordinary circumstances, if telemedicine is not possible, telephone assessment is permitted. Effort should be made to have the same assessor complete all post-Baseline visit assessments for an individual subject when possible. The possibility of a remote visit and the procedures to be conducted need to be discussed with the Sponsor in advance;
- For subjects in the sub-study only: perform a brain MRI-DTI;
- Measure health-related quality of life with the EQ-5D questionnaire;
- Record the date the subject was admitted to and/or discharged from the ICU, the hospital, and to a non-hospital residential care facility following the initial stroke;
- Inquire about rehabilitation activities (e.g., inpatient physical therapy, outpatient physical therapy, etc.);
- Inquire about occupational status (e.g., employed or retired, full or part-time status, etc.);
- Assess adverse events; and
- Record concomitant medications if the ET Visit occurs on or prior to Day 90 (ET Visit only).

7 EFFICACY ASSESSMENTS

7.1 Endpoints

7.1.1 Primary Efficacy Variable

The primary efficacy variable is the mRS score at Day 90. Differences between the MultiStem and placebo treatment groups in the distribution of Day 90 mRS scores will be evaluated by shift analysis.

7.1.2 Secondary Efficacy Variables

The key secondary efficacy variables are defined below. Differences between the MultiStem and placebo treatment groups will be evaluated using hierarchical testing.

- Proportion of subjects achieving an excellent outcome at Day 365 defined by all of the following criteria: mRS score of ≤1, NIHSS total score of ≤1, and Barthel Index score of ≥95;
- Proportion of subjects achieving an excellent outcome at Day 90 defined by all of the following criteria: mRS score of ≤ 1 , NIHSS total score of ≤ 1 , and Barthel Index score of ≥ 95 ; and
- Proportion of subjects with a mRS score of ≤ 2 at Day 90.

Other secondary efficacy variables will examine the difference between the MultiStem and placebo treatment groups for the following:

- Global disability throughout the range of mRS scores by shift analysis at Day 365;
- Proportion of subjects with a Barthel Index score of ≥95 at Day 90 and Day 365;
- Proportion of subjects with a NIHSS score of ≤1 at Day 90 and Day 365;
- Proportion of subjects with a mRS score of ≤1 at Day 90 and Day 365;
- Number of hospital-free days through Day 28;
- Number of ICU-free days through Day 28;
- Number of hospital-free days through Day 90;
- Number of hospital and non-hospital residential care-free days through Day 90;
- Proportion of subjects with all-cause mortality through Day 90;
- Proportion of subjects with secondary infections through Day 90;
- Proportion of subjects with urinary tract infections through Day 90; and
- Proportion of subjects who survived without life-threatening adverse events at Day 90.

7.1.3 Tertiary Efficacy Variables

Tertiary efficacy variables include the difference between the MultiStem and placebo treatment groups for the following:

- Changes in blood biomarkers (white blood cell populations and inflammatory markers) from Baseline to 48 hours from the start of the infusion and Day 7;
- Quality of life measured by the EQ-5D questionnaire at Day 90 and Day 365;
- Number of hospital and non-hospital residential care-free days through Day 365;
- Rehabilitation services utilization through Day 365;
- Changes in spleen size via exploratory imaging from Baseline to 24 hours from the start of the infusion, 48 hours from the start of the infusion and Day 7/discharge (sub-study at selected sites only); and
- Changes in white matter tract organization via exploratory imaging from Baseline to Day 90 and Day 365 (sub-study at selected sites only).

7.2 Assessments

7.2.1 National Institutes of Health Stroke Scale

The NIHSS assessment is a standardized method that uses a 42-point scale to measure the level of impairment caused by a stroke. The 42-point scale measures several aspects of brain function, including consciousness, vision, sensation, movement, speech, and language (0 = no stroke and 42 = severe stroke). Determination of NIHSS score will be performed at Screening (0 to 28 hours post-stroke), Baseline (Day 0 [18 to 34 hours post-stroke] before infusion start), Day 7, Day 30, Day 90, Day 180, and Day 365/ET.

The Screening NIHSS score used for determination of eligibility should be collected as soon as possible following admission to the hospital. In the event a subject receives concomitant reperfusion therapy the subject's Screening NIHSS score is encouraged to be collected prior to any concomitant reperfusion therapy but can be collected as late as 4 hours following completion of the last reperfusion (mechanical or pharmacologic) therapy. The Baseline NIHSS assessment should occur between 18 and 34 hours from the time of stroke onset and ≥6 hours after the last NIHSS assessment at Screening. The Baseline NIHSS score should not have changed by ≥4 points from the Screening NIHSS. The Baseline NIHSS score should be confirmed prior to randomization.

NIHSS assessments are preferred to be completed in a face-to-face setting. If conducted remotely, telemedicine is acceptable, and telephone is not acceptable. The possibility of a remote visit and the procedures to be conducted need to be discussed with the Sponsor in advance.

NIHSS assessments for post-Baseline visits must be completed by staff who are certified in NIHSS administration. Effort should be made to have the same assessor complete all post-Baseline visit assessments for an individual subject when possible.

7.2.2 Modified Rankin Scale

The mRS measures independence rather than performance of specific tasks. The mRS is not a patient-reported outcome, but should be administered by appropriate clinical site personnel based on the full exploration of the subject's current functional status at the time of the interview. This tool incorporates mental as well as physical adaptations to the neurological deficits. The scale consists of 7 grades, from 0 to 6, with 0 corresponding to no symptoms and 6 corresponding to death. Training for mRS administration will be provided along with guidance in the study manual.

Note: In exception to the above description, the premorbid mRS score determined at Screening is based on historical values prior to the onset of symptoms of the current stroke by either self-reported history or family/caregiver report while scores at subsequent visits are based on values obtained following the onset of the current stroke.

Assessments of the mRS score will be performed at Screening (0 to 28 hours post-stroke [prior to the onset of symptoms of the current stroke by either self-reported history or family/caregiver report]) for historical pre-stroke inclusion criterion and then at Day 7, Day 30, Day 90, Day 180, and Day 365/ET for efficacy.

Note: The mRS assessments are strongly preferred to be completed in a face-to-face setting. If face-to-face assessment is not possible, assessments may be conducted remotely by telemedicine. Only as a last resort in extraordinary circumstances, if telemedicine is not possible, telephone assessment is permitted. Effort should be made to have the same assessor complete all post-Baseline visit assessments for an individual subject when possible. The possibility of a remote visit and the procedures to be conducted need to be discussed with the Sponsor in advance. When evaluating subjects to determine the mRS score, the raters of the score must not make any attempt to exclude or correct for disability that the rater attributes to causes other than stroke. The score should be recorded without regard to the cause of the disabilities that impact the score or time point at which the disabilities occurred.

7.2.3 Barthel Index

The Barthel Index is an instrument used to measure a subject's performance in 10 activities of daily life. The items can be divided into a group that is related to self-care (feeding, grooming, bathing, dressing, bowel and bladder care, and toilet use) and a group related to mobility (ambulation, transfers, and stair climbing). The maximal score is 100 if 5-point increments are used, indicating the subject is fully independent in physical functioning. The lowest score is 0, representing a totally bedridden state. Assessments for Barthel Index score will be performed at Screening for historical pre-stroke inclusion criterion (0 to 28 hours post-stroke [prior to the onset of symptoms of the current stroke by either self-reported history or family/caregiver report]), Day 7, Day 30, Day 90, Day 180, and Day 365/ET. At Screening, the Barthel Index score can be collected any time prior to the start of the infusion.

Barthel Index assessments are strongly preferred to be completed in a face-to-face setting. If face-to-face assessment is not possible, assessments may be conducted remotely by telemedicine. Only as a last resort in extraordinary circumstances, if telemedicine is not possible, telephone assessment is permitted. The possibility of a remote visit and the procedures to be conducted need to be discussed with the Sponsor in advance.

Effort should be made to have the same assessor complete all post-Baseline visit assessments for an individual subject when possible.

7.2.4 EQ-5D Questionnaire

The EQ-5D questionnaire is a standardized instrument used to measure health outcome, specifically health-related quality of life in this study. The EQ-5D questionnaire will be administered at Day 90 and Day 365/ET.

7.2.5 Rehabilitation

Subjects will be asked about any rehabilitation activities that have taken place (e.g., inpatient physical therapy, outpatient physical therapy, etc.) at Day 7, Day 30, Day 60, Day 90, Day 150, Day 180, Day 210, Day 270, Day 330, and Day 365/ET.

7.2.6 Occupational Status

Questions about a subject's pre- and post-stroke occupational status (e.g., employed or retired, full or part-time status, etc.) will be asked at Day 365/ET.

7.2.7 Hospitalization

The date the subject has been admitted to and/or discharged from the ICU, hospital, and to a non-hospital residential care facility (such as in-patient rehabilitation, skilled nursing, or long-term acute care facility) should be recorded from the time of hospital admission to the clinical site following the initial stroke through Day 365.

For analysis, these data will be converted to ICU, hospital, and non-hospital residential care-free days to correct for the otherwise confounding effects of differential mortality on group hospital utilization data.

7.2.8 Exploratory Blood Marker Assessment

A blood sample for exploratory blood biomarker evaluation (white blood cell populations and inflammatory markers) will be drawn at Baseline (Day 0 before infusion start), 48 hours from the start of the infusion, and Day 7. For blood sampling procedures, including information on blood volume, collection tubes, sample processing, storage, and shipping, see the Laboratory Manual for this study.

7.2.9 Antibody Assessment

A blood sample for allogeneic antibody testing to MultiStem will also be drawn at Baseline (Day 0 before infusion start) and at Day 30.

7.2.10 Spleen Ultrasound (Sub-Study Only)

A spleen ultrasound will be performed for subjects in the sub-study at Baseline (Day 0 before infusion start), 24 hours from the start of the infusion, 48 hours from the start of the infusion, and Day 7/discharge to examine changes in spleen size via exploratory imaging.

7.2.11 Brain MRI-DTI (Sub-Study Only)

A brain MRI-DTI will be performed for subjects in the sub-study any time prior to the start of the infusion (considered Baseline), and then at Day 90 and Day 365/ET to examine changes in white matter tract organization via exploratory imaging.

8 SAFETY ASSESSMENTS

8.1 Adverse Events

A secondary endpoint in this clinical study will be the frequency and severity of adverse events through Day 365.

An adverse event is defined as any untoward medical occurrence in a clinical investigation subject administered a pharmaceutical product, which does not necessarily have a causal relationship with this treatment. An adverse event can therefore be any unfavorable and/or unintended sign (including an abnormal laboratory finding), symptom, or disease temporally associated with the use of an investigational medicinal product, whether or not related to the investigational medicinal product. All adverse events, including observed or volunteered problems, complaints, or symptoms, are to be recorded on the appropriate eCRF.

Adverse events, which include clinical laboratory test variables, will be monitored and documented from the start of the infusion at Day 0 until study participation is complete. Subjects should be instructed to report any adverse event that they experience to the Investigator. Beginning at the start of the infusion at Day 0, Investigators should make an assessment for adverse events at each visit and record the event on the appropriate adverse event eCRF.

Wherever possible, a specific disease or syndrome rather than individual associated signs and symptoms should be identified by the Investigator and recorded on the eCRF. However, if an observed or reported sign or symptom is not considered a component of a specific disease or syndrome by the Investigator, it should be recorded as a separate adverse event on the eCRF. Additionally, the condition that led to a medical or surgical procedure (e.g., surgery, endoscopy, tooth extraction, or transfusion) should be recorded as an adverse event, not the procedure.

Any medical condition already present at Screening or Baseline should not be reported as an adverse event unless the medical condition or signs or symptoms present at Baseline changes in severity or seriousness at any time during the study. In this case, it should be reported as an adverse event.

Clinically significant abnormal laboratory or other examination (e.g., ECG) findings that are detected during the study or are present at Baseline and significantly worsen during the study should be reported as adverse events. The Investigator will exercise his or her medical and scientific judgment in deciding whether an abnormal laboratory finding or other abnormal assessment is clinically significant. Clinically significant abnormal laboratory values occurring during the clinical study will be followed until repeat tests return to normal, stabilize, or are no longer clinically significant. Any abnormal test that is determined to be an error does not require reporting as an adverse event.

8.1.1 Adverse (Drug) Reaction

All noxious and unintended responses to a medicinal product related to any dose should be considered an adverse drug reaction. "Responses" to a medicinal product means that a causal relationship between a medicinal product and an adverse event is at least a reasonable possibility, i.e., the relationship cannot be ruled out.

8.1.2 Unexpected Adverse Drug Reaction

An Unexpected Adverse Drug Reaction is defined as an adverse reaction, the nature or severity of which is not consistent with the applicable product information. For MultiStem the reference safety information is included in Section 6.3 of the Investigator's Brochure currently in force. The reference safety information will be reviewed yearly and the periodicity of the review will be harmonized with the reporting period of the Development Safety Update Report.

8.1.3 Assessment of Adverse Events by the Investigator

The Investigator will assess the severity (intensity) of each adverse event as mild, moderate, or severe, and will also categorize each adverse event as to its potential relationship to investigational product using the categories of definitely, probably, possibly, unlikely, and unrelated.

8.1.3.1 Assessment of severity

- Mild An event that is easily tolerated and generally not interfering with normal daily activities.
- Moderate An event that is sufficiently discomforting to interfere with normal daily activities.
- Severe An event that is incapacitating with inability to work or perform normal daily activities.

8.1.3.2 Causality assessment

The relationship of an adverse event to the administration of the investigational product is to be assessed according to the following definitions:

- Definitely related: Follows a reasonable temporal sequence from investigational product administration; abates upon discontinuation of the investigational product (dechallenge); and is confirmed by reappearance of the reaction on repeat exposure (rechallenge);
- Probably related: Follows a reasonable temporal sequence from investigational product administration, abates upon discontinuation of the investigational product (dechallenge), and cannot be reasonably explained by the known characteristics of the subject's clinical state;
- Possibly related: Follows a reasonable temporal sequence from investigational product administration and could have been produced by the subject's state or by other modes of therapy administered to the subject;
- Unlikely related: The temporal sequence between the adverse event and the investigational product administration is such that the drug is not likely to have had any reasonable association with the observed event and the adverse event could have been produced by the subject's clinical condition or by other modes of therapy administered to the subject; or
- Unrelated: The adverse event is definitely produced by the subject's clinical condition or by other modes of therapy administered to the subject and the adverse event does not follow a temporal sequence from investigational product administration.

The following factors should also be considered:

- The temporal sequence from investigational product administration-
 - The event should occur after the investigational product is given. The length of time from investigational product exposure to event should be evaluated in the clinical context of the event.
- Underlying, concomitant, intercurrent diseases
 - o Each report should be evaluated in the context of the natural history and course of the disease being treated and any other disease the subject may have.
- Concomitant drug
 - o The other drugs the subject is taking or the treatment the subject receives should be examined to determine whether any of them might be recognized to cause the event in question.
- Known response pattern for this class of investigational product
 - o Clinical and/or non-clinical data may indicate whether a particular response is likely to be a class effect.
- Exposure to physical and/or mental stresses
 - o The exposure to stress might induce adverse changes in the recipient and provide a logical and better explanation for the event.
- The pharmacology and pharmacokinetics of the investigational product-
 - The known pharmacologic properties (absorption, distribution, metabolism, and excretion) of the investigational product should be considered.

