4.4 Enrollment Stopping Rules

An independent DSMB will meet after approximately one-third and approximately two-thirds of the subject enrollment are complete to examine unblinded safety data. See Section 9.2.4 for details about the DSMB. The stopping rules for the study include any of the following until the DSMB determines if it is safe for the study to continue enrollment:

- Serious adverse event (SAE) assessed through 3 days post-infusion that is related to investigational product; and/or
- Any Grade 3 or 4 infusion-related reaction (Common Terminology Criteria for Adverse Events v4.0) in the first 24 hours post-infusion (see Appendix B for definitions and management of Grade 2 and 4 infusion-related reactions).

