5 STUDY TREATMENTS

5.1 Treatment Groups

Subjects will be randomly assigned to receive a single IV infusion of MultiStem or matching placebo at Baseline (Day 0 [18 to 36 hours post-stroke]). MultiStem will be provided in a 1.2 billion cell dose $\pm 20\%$.

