5.5.3 Investigational Product Administration

Subjects will receive a single IV infusion of MultiStem or matching placebo at Baseline (Day 0 [18 to 36 hours post-stroke]).

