9.2.2.1 Adverse events

Adverse events will be coded using the Medical Dictionary for Regulatory Activities (MedDRA). An overview of adverse events categories will be summarized with counts and percentages. Categories will include:

- Treatment-emergent adverse event (TEAE);
- Investigational product related (definitely, probably, possibly, unlikely, unrelated);
- Infusion-related allergic reaction;
- Neurological worsening;
- Secondary infection;
- Urinary tract infections;
- Maximum severity of TEAE mild, moderate, severe, life-threatening, or death; and
- Serious TEAE.

Adverse events will also be summarized by system organ class and preferred term with counts and percentages. Similar summaries will be provided for:

- Serious TEAEs;
- Investigational product-related TEAEs;
- Infusion-related TEAEs;
- Neurological worsening TEAEs; and
- Secondary infections.

Infusion-related TEAEs will be identified on the eCRF. Secondary infections will be identified by a review of the coded adverse events by the medical monitor prior to database unblinding.

Similar adverse event overview and summary tables will be provided for adverse events within 7 days of treatment infusion and within 90 days of treatment infusion.

Analysis listings of SAEs, investigational product-related adverse events, infusion-related allergic reaction adverse events, and neurological worsening adverse events will be provided by treatment group. The analysis listings will include a treatment-emergent flag, reported term, system organ class, preferred term, start date and time, stop date, severity, relation to investigational product, action taken, outcome, seriousness, dechallenge result, and rechallenge result as appropriate.

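### The causality definitions leave no category for a post-infusion event with plausible timing and no other explanation, and 'related' is never tied to the categories that count

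*Protocol*

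**What the plan says.** Sections 5.1 and 5.5.3 give each subject one exposure: "Subjects will receive a single IV infusion of MultiStem or matching placebo at Baseline".

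Section 8.1.3.2 defines five causality categories. *Definitely related* needs plausible timing, abatement on discontinuation, and an event that "is confirmed by reappearance of the reaction on repeat exposure (rechallenge". *Probably related* needs plausible timing and an event that "abates upon discontinuation of the investigational product (dechallenge), and cannot be reasonably explained" by what is known of the subject's clinical state. *Possibly related* needs plausible timing and that the subject's state or another therapy could have been the cause. *Unlikely* and *unrelated* both need timing that argues against the product together with another possible or definite cause.

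The rating is then used elsewhere:

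- Section 4.4 halts enrollment pending DSMB review for a "Serious adverse event (SAE) assessed through 3 days post-infusion that is related to investigational product".
- Section 8.3.3 defines a SUSAR through an association with the study drug.
- Section 9.2.2.1 lists all five categories in the overview and also summarizes product-related TEAEs.
- Section 5.4 asks for the rating before emergency unblinding.

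None of these says which categories make an event related. Section 8.1.1 gives a separate test for an adverse reaction: a causal link that is a reasonable possibility and has not been excluded.

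On severity, section 8.1.3 has the investigator record the "severity (intensity) of each adverse event as mild, moderate, or severe", with definitions for those three levels in 8.1.3.1. Section 9.2.2.1 tabulates maximum severity as "mild, moderate, severe, life-threatening, or death".

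**The concern.** Dechallenge and rechallenge are criteria for a product that is given repeatedly and can be withdrawn. Here the exposure is a single infusion, and the safety question runs well past its end: section 4.4 looks at serious events through 3 days, and adverse events are collected through Day 365. If the two strongest categories depend on manoeuvres that are unavailable after the infusion, and the third presupposes a rival explanation, the clearest late signal has nowhere to go. Investigators would have to improvise, probably differently from site to site, on a field that feeds an enrollment halt, expedited reporting and the related-event tables.

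The undefined cut-off adds to this. Whether a serious event on the day after infusion stops enrollment depends on whether *possibly related* counts, and section 4.4 does not say.

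The severity mismatch is a smaller, separate matter: two of the tabulated levels are not on the scale that investigators use, and a secondary endpoint, "Proportion of subjects who survived without life-threatening adverse events at Day 90", refers to one of them.

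**Working it through.** No arithmetic beyond counting applies. The check is to take an event with plausible timing and ask which category it can enter under section 8.1.3.2 as written.

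**Step 1: what can be withdrawn or repeated.** During the infusion, Appendix B foresees, for a Grade 2 reaction, slowing, stopping, resuming at a reduced rate, and recurrence. Dechallenge, and a form of re-exposure, can therefore occur. For Grade 3 or 4 reactions Appendix B discontinues treatment, so re-exposure does not follow. Once the infusion has ended, nothing is left to discontinue or repeat.

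**Step 2: reachable categories for an event with plausible timing.**

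| Onset | Another cause possible? | Definitely | Probably | Possibly | Unlikely / unrelated |
|---|---|---|---|---|---|
| During infusion | No | Only if it abates on stopping and recurs on resumption | Yes, if it abates on stopping | No, needs a possible other cause | No, timing fits the product |
| During infusion | Yes | As above | Only if the clinical state is not a reasonable explanation | Yes | No |
| After infusion | Yes | No | No | Yes | No |
| After infusion | No | No, neither dechallenge nor rechallenge available | No, dechallenge unavailable | No, needs a possible other cause | No, timing fits the product |

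The last row is empty: 0 of 5 categories fit. In both post-infusion rows, 2 of the 5 categories (*definitely*, *probably*) are closed by definition.

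**Step 3: where the rating is used.** Set sections 4.4, 8.3.3 and 9.2.2.1 beside 8.1.1.

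- If 'related' means *probably* or *definitely*, a serious event starting after the infusion cannot literally meet the first trigger in 4.4.
- If 'related' includes *possibly*, as the wording of 8.1.1 suggests, a post-infusion event with a competing stroke-related explanation can meet it. The unexplained event in the last row still has no category.

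The protocol does not say which reading applies, and the last row stays empty under both.

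**Step 4: severity.** Levels recorded (8.1.3, 8.1.3.1): 3. Levels tabulated (9.2.2.1): 5. Levels with no source on the severity scale: 5 − 3 = 2, namely life-threatening and death. Section 8.2 defines the first and lists the second, but as seriousness criteria. No passage links those criteria to the severity table or to the Day 90 endpoint.

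**The case against.** The strongest reply is that the practical harm is limited, and much of that reply stands.

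- A reader might infer that *definitely related* can never be reached by any of the roughly 300 subjects. Appendix B does not support that: a reaction that subsides on stopping and returns on resumption meets the wording, however rarely.
- A reader might infer that the first trigger in 4.4 is closed for almost all of its 3 days. The protocol gives no infusion duration from which to compute such a share. The closure also depends on reading 'related' as *probably* or above, which 4.4 does not say and 8.1.1 argues against.
- A reader might infer that the enrollment halt and the related-event tables rest on unreachable categories. They do not: *possibly related* needs neither dechallenge nor rechallenge, and subjects treated 18 to 36 hours after a cortical stroke will often have a competing explanation that makes it available.
- There are backstops. The second trigger in 4.4 (Grade 3 or 4 infusion-related reactions in the first 24 hours) is based on grade and not on these categories, and the DSMB sees unblinded safety data at about one-third and two-thirds of enrollment. The first of these covers infusion-related reactions only, so it does not replace the 3-day rule for serious events.
- Section 8.1.3.2 also tells investigators to weigh timing, concurrent disease, other drugs and class effects. That guides judgment but does not change the conditions attached to each category.
- The life-threatening endpoint has a source in the seriousness criteria of 8.2, so it is not left without data. Only the mapping is unstated, and a SAP or eCRF guideline could supply that.

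What the reply does not remove is the empty row, the missing meaning of 'related', and the two conflicting severity scales. The causality definitions and the enrollment trigger are instructions to sites and belong in the protocol. Under 9.2.4 enrollment stops before the DSMB reviews, so the meaning of 'related' must be settled beforehand.

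**Conclusion.** The point holds as a defect of definition. As written, a post-infusion event with plausible timing and no alternative explanation fits none of the five causality categories, and the protocol does not say which categories count as related for the enrollment halt, SUSAR handling or the related-TEAE tables. The severity scales in 8.1.3 and 9.2.2.1 contradict each other by two levels.

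The conclusion assumes that investigators apply the definitions literally. In practice some would choose *possibly* or *probably* for such an event, so how many events would be misfiled cannot be derived from the protocol, and no under-recording is demonstrated. It also allows that eCRF guidance or a SAP, neither of which is shown, may supply the severity mapping. The primary and key secondary efficacy analyses are not affected. The documents do not support the stronger conclusion that the stopping rule cannot work or that the product-related tables would be empty.

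**What to change.** 1. Reword the definitions in 8.1.3.2 for a single infusion. Base them on timing, plausibility and alternative causes, and treat dechallenge and rechallenge as supporting evidence only where applicable. Check that every event with plausible timing and no alternative cause falls in a related category.
2. State once which categories make an event related, and reconcile sections 4.4, 8.1.1, 8.3.3 and 9.2.2.1 to that statement. Which cut-off applies to the enrollment halt is for the sponsor and the DSMB to decide; the need is that it be stated and consistent.
3. Reconcile 8.1.3 and 8.1.3.1 with 9.2.2.1. One way is to tabulate three severity levels and take life-threatening and fatal status from the seriousness criteria in 8.2, naming that as the source for the Day 90 endpoint in 7.1.2. Another is to add the two levels to the recorded scale.

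The cost is protocol and eCRF-guideline wording, with no extra visits or staff. The downside is that somewhat more events may be rated related, with slightly more frequent DSMB reviews.
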